## C Study Objectives

#### C1 Study Aims and Rationale for Selection of Outcome Measures

Aim 1: Establish feasibility of a definitive trial by determining the proportion of eligible subjects who agree to randomized treatment and determining the followup retention rate. Rationale: To date, no studies have compared IB and LRTI for thumb CMC OA. Our study will assess the feasibility of a prospective RCT comparing outcomes of the two procedures. Hypothesis: A prospective RCT comparing outcomes of IB and LRTI is feasible, as defined by the ability to successfully recruit and randomize  $\geq$ 50 patients over the course of 1 year with a follow-up retention rate of  $\geq$ 90%.

Aim 2: Estimate effect sizes and variability in patient-reported outcomes for planning a definitive, two-arm RCT. Rationale: We will assess patient-reported outcomes (PROMIS UE/physical function, VAS pain, VAS satisfaction) following IB and LRTI. Effect size and variability estimates are required to inform the design of a future definitive trial. Hypothesis: IB will produce superior patient-reported outcomes to those of LRTI at 6 weeks and 3 months.

Aim 3: Characterize objective clinical outcomes (thumb range of motion, grip/pinch strength, radiographic outcomes, and complications/need for additional surgery) and to identify differences in return to work/activity following IB and LRTI at three months. Rationale: Objective clinical outcomes are important predictors of patient function after surgery for thumb CMC OA. IB offers an expedited return to work and activity by allowing patients to forego postoperative casting. Hypothesis: IB will produce similar objective outcomes to LRTI with a quicker return to work/activity.

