Patients will undergo a standardized postoperative recovery and therapy regimen:

#### Study Aims 2 & 3

PROMIS Physical Function and Upper Extremity scores will be collected at all clinic visits on iPad as per standard protocol for all patients presenting to a Washington Orthopaedic Surgery clinic. Thumb Universitv ROM at carpometacarpal. metacarpophalangeal, and interphalangeal joints will be collected by a member of our team at 4 weeks, 3 months, and 1 year after surgery. Visual Analog Scale Pain and Satisfaction scores will be collected by a member of our team at 2 weeks, 4 weeks, 3 months, and 1 year post-op. Grip and pinch strength (3-point and lateral vs contralateral values and vs preoperative values) will be collected at pre-op visit and all post-op visits except the 2 week visit. Radiographic subsidence will be measured via C-arm radiographs at 3 months and 1 year post-op. Complications (mild, moderate, severe) will be recorded throughout the course of the study at all time points. Mild complications will be defined as those with minor clinical impact (i.e., scar tenderness or sensory disturbances). Moderate complications will be defined as clinically relevant with delay in patient recovery, but not severe enough to necessitate revision surgery and resolve by 12 months after surgery (i.e., mild CRPS type I, tendinitis, neuromas treated with steroid injections). Severe complications will be defined as those which result in revision surgery, pain at rest, or impaired hand function at 12 month exam (i.e., severe CRPS) type I or tendinitis and neuromas that do not improve with corticosteroid injections and require surgery). We will document patient return to work/activity at each follow-up appointment.

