# F Statistical Plan

## *F1* Sample Size Determination and Power

Various methods are identified in the literature for formulating a pilot study sample size. Julious recommends a minimum sample size of 12 per group as a rule of thumb and justifies this based on rationale about feasibility and precision about the mean and variance. So as to align our study with these recommendations, we plan to enroll 50 patients total in our pilot/feasibility study.

Approximately 100 patients per year undergo surgical intervention (either IB or LRTI) for CMC OA at Washington University. Assuming a 50% randomization rate for this study, a sample size of 100 produces a two-sided 95% confidence interval with a lower limit of 0.404 and upper limit of 0.596 when the sample proportion is 0.5. The primary goal of the trial is to assess feasibility and to obtain estimates for planning a larger, more definitive study to detect meaningful changes in clinical outcome measures.

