## F2 Analysis Plan and Statistical Methods

Patient demographic and clinical characteristics will be summarized using means (standard deviation, SD) or median (25th, 75th) for continuous variables and frequency (percentage) for categorical variables. The recruitment rate (95% confidence interval) will be reported as the number randomized out of the total number of participants approached to participate in the study (screened). Reasons for not wanting to participate will be summarized and reported. The effect sizes and variability of the PROMs for each group will be reported and used to determine the sample size for a larger definitive trial. Differences in PROMs between LRTI and IB at 6 weeks and 3 months will be examined using a two-sample t-test and differences in categorical outcomes (return to work/activity, yes/no, at 3 months) using Pearson chi-squared test. Changes over time will be evaluated graphically to see the trajectory of change over follow-up and for assessing critical time points to inform future study design parameters. Objective parameters will be summarized for each group using descriptive statistics. The significance level will be 0.05 for all tests due to the exploratory nature of the study.

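### Aim 3 hypothesizes similar objective outcomes in the two arms, but F2 plans only per-group summaries of them, with no between-arm estimate

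*Combined protocol and SAP*

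**What the plan says.** In C1, Aim 3 has two parts. The first is descriptive: "Characterize objective clinical outcomes (thumb range of motion, grip/pinch strength, radiographic outcomes, and complications/need for additional surgery", where the list closes. The second is to find differences in return to work or activity. The hypothesis attached to the aim compares the arms on both parts: "IB will produce similar objective outcomes to LRTI with a quicker return to work/activity".

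F2 then sets out the analyses:

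- Patient-reported outcomes: "Differences in PROMs between LRTI and IB at 6 weeks and 3 months will be examined using a two-sample t-test".
- Categorical outcomes: "differences in categorical outcomes (return to work/activity, yes/no, at 3 months) using Pearson chi-squared test". Return to work/activity is the only outcome named.
- Objective outcomes: "Objective parameters will be summarized for each group using descriptive statistics".
- Error rate: "The significance level will be 0.05 for all tests due to the exploratory nature of the study".

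D1 and E2 say that grip and pinch strength "will be collected at pre-op visit and all post-op visits except the 2 week visit". The comparisons they name for strength are with the opposite hand and with the pre-operative value.

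**The concern.** A hypothesis that two arms are similar is a statement about the difference between them. For range of motion, grip, pinch, subsidence and complications, the plan does not produce that difference or any measure of its uncertainty. The strength comparisons in D1 and E2 are within patients, so they do not fill the gap.

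The risk lies in how the results will be read. Two columns of summaries that look alike invite the word similar, and nothing beside them shows how large a deficit the data still allow. B1 makes this more than a formality. It reports that tendon suspension is used in the belief that it limits subsidence and improves pinch strength, and it treats the objective measures as critical to judging IB against LRTI.

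The pre-operative grip and pinch values, already collected, also enter no between-arm estimate.

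**Working it through.** **The plan's own figure.** The only precision figure in the plan is for the randomization rate in F1: 0.404 to 0.596 at n = 100 and proportion 0.5. The Wilson score interval reproduces it (0.4038 to 0.5962). It does not bear on this point, and no precision figure is given for any objective outcome.

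**Inputs.**

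- Total sample size, from F1: "we plan to enroll 50 patients total in our pilot/feasibility study".
- Allocation: the ratio is not stated; 1:1 is assumed, giving 25 per arm.
- Retention: the feasibility criterion in C1 is at least 90%, so 0.90 × 50 = 45 patients, taken as 23 and 22. A slightly worse case of 22 per arm is also shown.
- SDs, complication rates and pre/post correlations: none are given. Results are in SD units or over assumed ranges.

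**1. Precision of a mean difference.** The 95% half-width in SD units is t(0.975, n1 + n2 − 2) × √(1/n1 + 1/n2).

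- 25 vs 25: t(48) × √(2/25) = 0.569
- 23 vs 22: t(43) × √(1/23 + 1/22) = 0.601
- 22 vs 22: t(42) × √(2/22) = 0.608

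If the two observed means were identical, the interval would run from about −0.57 to +0.57 SD at best.

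**2. Precision of a complication risk difference.** The approximate half-width is 1.96 × √[p(1 − p)(1/n1 + 1/n2)], for an assumed common rate p.

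| Assumed rate | 25 vs 25 | 23 vs 22 |
|---|---|---|
| 10% | ±17 points | ±18 points |
| 20% | ±22 points | ±23 points |
| 30% | ±25 points | ±27 points |

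These are Wald approximations and are rough at the lowest rate, where 0.10 × 25 = 2.5 events are expected per arm.

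**3. What baseline adjustment could add for grip and pinch.** The variance is multiplied by 1 − ρ² and the half-width by √(1 − ρ²), where ρ is the pre/post correlation.

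- ρ = 0.5: √0.75 = 0.866, so the CI narrows by about 13% (0.569 to about 0.49 SD)
- ρ = 0.6: √0.64 = 0.80, so the CI narrows by 20% (0.569 to about 0.46 SD)

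Both correlations are assumptions.

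**4. Could 50 patients establish similarity?** The plan sets no margin. Take an illustrative margin of 0.5 SD, two one-sided tests at 0.05 and a true difference of zero. Simulated power is then about 10% at 25 per arm and 6% at 23 vs 22. At a margin of 0.8 SD it is 75% and 68%.

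**The case against.** The best defence is that F2 follows the aim as worded. Aim 3 sets out to characterize objective outcomes and to find differences in return to work. F2 gives the first a description and the second a between-arm test. The study is a pilot whose primary goal is feasibility and planning estimates. The central hypothesis in A2 and the expected conclusions in A1, A3 and B1 do not include similar objective outcomes, and F2 contains no rule for declaring similarity. All of this stands, and it limits the conflict to one hypothesis sentence and one analysis sentence. It does not remove the conflict: the hypothesis is comparative, and F2 already accepts between-arm analysis in this pilot for other outcomes.

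A reader might infer that the trial cannot answer Aim 3 at all. The documents do not support that, because return to work/activity has its own between-arm test.

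A reader might also infer that the between-arm information is lost. That is too strong as well. If means, SDs and numbers are reported by arm, an unadjusted difference and interval can be derived, and complication counts give a risk difference directly. Two limits remain: F2 does not say which descriptive statistics the objective outcomes will get, and medians with quartiles would not allow the derivation directly. The baseline-adjusted difference could not be recovered from such summaries.

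It is also fair to object that the remedy adds many intervals. Three thumb joints, grip, two pinch types and subsidence at two times make 7 × 2 = 14, plus complications. They must be labelled exploratory.

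**Conclusion.** The point holds as a mismatch between hypothesis and analysis for the objective-outcome half of Aim 3. Feasibility, Aim 2 and the return-to-work test are unaffected.

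The uncertainty that the planned summaries would leave unstated is about 0.57 to 0.61 SD either side of a mean difference before adjustment, assuming 1:1 allocation and 22 to 25 patients per arm. For complications it is about 17 to 27 percentage points, at assumed rates of 10% to 30%. Any gain from baseline adjustment depends on the assumed correlation.

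Two further readings should be resisted. One is that an added interval would let the trial confirm similarity. It would not: power at a 0.5 SD margin is about 6% to 10%, and a non-significant test would be no better evidence. The interval shows what remains possible. The other is that the definitive trial cannot be sized without these estimates. F2 says that the patient-reported outcomes will determine that sample size.

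**What to change.** In F2, replace the sentence on objective parameters with wording such as:

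*Objective outcomes will be summarized by group. For range of motion, grip, pinch and subsidence at 3 months and 1 year, the IB-minus-LRTI mean difference will be reported with its 95% CI; grip and pinch differences will be adjusted for the pre-operative value. For complications, the risk difference will be reported with its 95% CI. These intervals are exploratory and not adjusted for multiplicity. A sample of 50 cannot establish similarity, and similarity will not be concluded from the absence of a visible or statistically significant difference.*

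In C1, reword the Aim 3 hypothesis for objective outcomes as estimation, for example: to estimate the between-arm difference in each objective outcome and its precision. The return-to-work part can stay as it is.

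The cost is some protocol wording and a few lines of analysis code. All variables are already collected at these visits, and no procedure or sample size changes. The downside is a set of exploratory intervals that must not be read as confirmatory.

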# G Data Handling and Record Keeping

## G1 Confidentiality and Security

Only the minimum necessary private information is collected for the purposes of the study. Any procedures or interventions conducted as part of the study will be conducted in private setting to the extent possible. Recruitment/consent will occur in a private setting. Participants will be able to ask questions in a private setting. All materials are stored in secured environment and access is limited to research team members only. Our data will be stored in REDCap.

## H2 Funding Source and Conflicts of Interest

An American Foundation for Surgery of the Hand Fast Track Grant (\$5000) application was submitted for this study on 9/8/2019. Funding decisions will be announced in December 2019. The remainder of the study costs will be funded by the Washington University Department of Orthopaedic Surgery.

#### H3 Subject Stipends or Payments

Subjects will not receive compensation to participate in the study.

#### H4 Study Timetable

	6 months	12 months	24 months
Specific Aim 1	Patient enrollment, surgeries, data collection	Statistical analysis, manuscript writing and submission	Dissemination of study findings, future definitive RCT planning and execution
Specific Aim 2	Patient enrollment, surgeries, data collection	Statistical analysis, manuscript writing and submission	Dissemination of study findings, future definitive RCT planning and execution
Specific Aim 3	Patient enrollment, surgeries, data collection	Statistical analysis, manuscript writing and submission	Dissemination of study findings, future definitive RCT planning and execution

## I Publication Plan

We plan to publish our study's findings in a major journal such as Journal of Bone and Joint Surgery or the Journal of Hand Surgery.

## J Attachments

#### J1 Informed consent documents

Please refer to "Consent Documents & Other Attachments" section of IRB proposal for document entitled "LRTI IB Consent V1".

#### J2 Patient education brochures

Please refer to "Consent Documents & Other Attachments" section of IRB proposal for document entitled "2 Surgical Ooptions for Base of the Thumb Arthritis".

